3.2 Scientific Rationale for Study Design

This is a PROBE design- Prospective Randomized Open Label Blinded Endpoint Design, i.e. Treatment—is open label with respect to patient and investigators but is blinded to the endpoint committee. 8/10 Fingernails per participant will be randomized to receive treatment with plateletrich plasma and the remaining 2 nails will receive injections with platelet-poor plasma. Potential problems with the control group include nonuniform results due to the lack of response for the 2 nails receiving injections with platelet-poor plasma.

3.3 Justification for Dose

The nail matrix, located at the proximal nail fold, functions as the nail growth center. We hypothesize that injecting 0.1-0.2 ml of platelet-rich plasma in this area will promote nail growth. On the other hand, injecting platelet-poor plasma, which lacks bioactive agents compared with the platelet-rich section, should not promote nail growth.

3.4 End of Study Definition

A participant is considered to have completed the study if he or she has completed all phases of the study including the last visit. The end of the study is defined as completion of the last visit or procedure.

4. Subject Selection

4.1 Study Population

Subjects with a diagnosis of brittle nail syndrome in all 10 fingernails who meet the inclusion and exclusion criteria will be eligible for participation in this study.

4.2 Inclusion Criteria

- 1. Patients who have been diagnosed with brittle nails
- 2. Must understand and voluntarily sign an informed consent form
- 3. Must be male or female and aged 18-95 years at time of consent
- 4. Must be able to adhere to the study visit schedule and other protocol requirements
- 5. A nail clipping with histopathology that is negative for the presence of dermatophyte infection
- 6. Patient must present with at least a score of 2 on the PGA scale.

4.3 Exclusion Criteria

- 1. Inability of the patient to provide written informed consent for any reason.
- 2. Subject has psoriasis, lichen planus, dermatophyte infection or other confounding abnormalities that are severe enough to result in a clinically abnormal fingernail
- 3. Use of any medication within 90 days prior to start of study
- 4. Inability to abstain for nail polishes, nail gels during the study period
- 5. Subject is pregnant or planning pregnancy.

4.4 Lifestyle Considerations

During this study, participants are asked to:

 Abstain from using any medication, moisturizers, oils, or nail polishes during the study period. Participants that do not fulfill this criterion will be excluded from the study.

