1.2.4 Primary Endpoints

The Primary efficacy endpoint will be the change in the Physician Global Improvement Assessment (PGIA) of the 8 target nails from baseline to weeks 12 – 14 of follow up to determine efficacy of PRP injection in the treatment of brittle nail syndrome.

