2.3 Rationale

Nail Plate (NP) brittleness is a very common nail complaint, with up to 20% of the population

experiencing some form of brittleness in their nails and is much more common for women over 50[1]. Nail brittleness is characterized by nails that split, flake and crumble, become soft and lose elasticity. All the signs of Brittle Nail Syndrome can be present at once or only partially present. Brittle Nail syndrome itself does not cause any pain, however it can cause functional problems due to the inability to use the nail and cosmetic problems, which can distress the patient [2]. Pain can occur due to the splitting of the nail, and in some studies, it correlates to depression in patients [3]. The most common cause of brittle nails is idiopathic, and the mechanism is poorly understood, it may have to do with the water content in the nails [4], but there very few studies in the area. Inflammatory disease such as psoriasis, lichen planus, lichen stratus, alopecia areata, Darier's disease and eczema can also cause secondary Brittle Nail syndrome. When Brittle Nail Syndrome is caused by an inflammatory disease, treatment of the underlying condition can help with Brittle Nail syndrome, however most patients have idiopathic Brittle Nail Syndrome and there is no effective treatment for the condition [5]. Biotin has been suggested as a treatment; however, it is poorly studied and the FDA issued an warning suggesting that biotin can cause interference with laboratory testing [6,9,10]. PRP injections have been used successful in other dermatological conditions such as androgenetic alopecia [7] and non-dermatological conditions like sports-related muscle, tendon and ligament injuries [8]. Platelet-rich plasma (PRP) is an autologous concentration of platelets, which can release quantities of growth factors and cytokines. As previously reported, such a complex of bioactive agents can promote the healing and restoration of multiple tissues when injured. PRP injection into the nail matrix may help promote growth of health nails in patients with idiopathic Brittle Nail syndrome by releasing growth factors and cytokines.

References:

- 1. Chen, P., et al., Intra-articular platelet-rich plasma injection for knee osteoarthritis: a summary of meta-analyses. J Orthop Surg Res, 2019. 14(1): p. 385.
- 2. Chessa, M.A., et al., Pathogenesis, Clinical Signs and Treatment Recommendations in Brittle Nails: A Review. Dermatol Ther (Heidelb), 2019.

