3.1 Overall Design

This is a single center evaluation of 10 patients with signs and symptoms of brittle nails. Patients will be consented and 8/10 fingernails will be treated with PRP and 2/10 fingernails will be used as controls. Computer software will be used to randomly generate a randomization table for each participant. Randomization for each participant will be done on the same day of their first treatment, after all inclusion and exclusion criteria, including a negative histopathology report for onychomycosis are fulfilled. Blood will be drawn from a vein in the patient's arm into a 11 ml Eclipse PRP Tube. The blood is processed using a centrifuge machine from eclipse medical. After centrifugation, the platelet poor portion will be separated from the platelet-rich portion. The proximal nail folds are cleansed with alcohol. Using a 1ml syringe and 30g needle, 0.1-0.2 ml of platelet-rich plasma is injected into 8 proximal nail folds (treated nails), while 2 proximal nail folds (untreated nails) are injected with platelet-poor plasma. The study patients will be treated with PRP injections monthly for 3 months. Study patients may not have used any medications on the nails 3 months prior to the study or nail polish 1 month prior to the study. The patient must abstain from using any medication, moisturizers, oils, or nail polishes during the study period. The primary efficacy

endpoint will be the individual physician observed Physician Global Improvement Score (PGIA), which encompasses observed improvement of lamellar splitting, transverse splitting, ridges and longitudinal grooves, longitudinal splitting, and nail thickness of target nails. This is a PROBE design- Prospective Randomized Open Label Blinded Endpoint Design, i.e. Treatment is open label with respect to patient and investigators but is blinded to the endpoint committee. High quality images will be obtained utilizing a Canon camera and reviewed by an independent blinded endpoint committee (3 dermatologists with expertise in nails disease [name], [name], and [name] [name]) for PGIA (Physician Global Improvement Assessment. If necessary due to poor image quality (e.g. light source not properly deployed), exposure correction post-imaging may be applied to images that are deemed unsatisfactory. The present study Is not funded, Eclipse Medical provided the required PRP kits, including the sterile tubes.

PGA (Physician Global Assessment) Score:

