6.1.2 Treatment Phase

The 10 fingernails of each participant will be randomly assigned to treatment with platelet-rich plasma or platelet-poor plasma (placebo) treatment groups in a 8:2 ratio using a computer-generated randomization scheme developed by the data manager.

Study Visits Visit 1: Week 0 - 2

Subjects who fulfill all inclusion and exclusion criteria, and sign informed consent are eligible to enroll and begin Visit 1 procedures that same day. For those patients that do not have a negative histopathology result for onychomycosis within the past 6 months, a nail clipping is obtained during screening visit and visit 1 procedure will take place in week 2 assuming the patient fulfill all inclusion and exclusion criteria.

Visit 1 Procedures:

- Patient Instructions
- Take High resolution digital photographs
- Randomization of participants that fulfilled all inclusion and exclusion criteria
- First Injection of PRP

Visits 2 and 3: Week 4 - 6 (±7 days) and Week 8 - 10 (± 7 days) The following procedures will be performed on these visits:

Second and third injections of PRP

- Review of eligibility criteria including review of concomitant medications/cosmetics
- · Collection of adverse events
- Take High resolution digital photographs

Visit 4: Week 12 – 14 (± 7 days) Collection of adverse events

- Take High resolution digital photographs
- Collection of Patient Satisfaction Survey

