7.8 General Concomitant Medication and Supportive Care Guidelines

All concomitant medications will be recorded and/or updated on subject medication chart throughout the course of the study and saved in subject binder, if applicable.

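### Restriction and recording rules do not say whether oral supplements such as biotin count, so a supplement effect could be credited to PRP and might not be captured

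*Combined protocol and SAP*

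**What the plan says.** Section 2.3 (Rationale) raises biotin as a candidate treatment for brittle nails: "Biotin has been suggested as a treatment; however, it is poorly studied". The rules that keep other nail treatments out are these:

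- **Before the study.** Section 4.3 excludes "Use of any medication within 90 days prior to start of study", and section 8 repeats this. Section 3.1 words the same washout more narrowly: "Study patients may not have used any medications on the nails 3 months prior to the study".
- **During the study.** Section 4.4 asks participants to "Abstain from using any medication, moisturizers, oils, or nail polishes during the study period", and adds: "Participants that do not fulfill this criterion will be excluded from the study". Sections 4.3 and 8 also mention nail gels.
- **Recording.** Section 6.1.2 lists for Visits 2 and 3 "Review of eligibility criteria including review of concomitant medications/cosmetics". Section 7.8 says "All concomitant medications will be recorded and/or updated on subject medication chart throughout the course of the study". Table 1 schedules concurrent medications at screening and Visits 1 to 4.

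Supplements, vitamins and biotin appear in none of these rules.

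The primary endpoint (section 1.2.4) is the PGIA change "of the 8 target nails from baseline to weeks 12 – 14 of follow up to determine efficacy of PRP injection". Section 12.1 compares follow-up with baseline in the PRP nails and, separately, in the PPP nails. It states no test of PRP against PPP.

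**The concern.** The lists go well beyond drugs, to moisturizers, oils, polishes and gels. The evident aim is to keep out anything that could change the nails during the study. The one competing product class that the protocol itself discusses is not mentioned, and its status depends on how each member of staff reads any medication. One could enrol a biotin user whom another would exclude. Because a breach of section 4.4 leads to exclusion, the reading also affects who is analysed.

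An oral product would be expected to reach all ten nails. A before/after test on the PRP nails cannot tell its effect from a PRP effect. If supplement use is not asked about during the visits, it cannot be reliably reconstructed afterwards.

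**Working it through.** **1. What each rule does with an oral supplement**

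| Rule | Scope | Covers oral biotin? |
|---|---|---|
| 4.3 and 8, pre-study | any medication, 90 days | unclear |
| 3.1, pre-study | medications on the nails, 3 months | no |
| 3.1 and 4.4, on study | any medication, plus moisturizers, oils, polishes | unclear |
| 6.1.2, Visits 2 and 3 | medications and cosmetics | unclear |
| 7.8 and Table 1 | medications | unclear |

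Resolving the conflict between 3.1 and 4.3 would not by itself settle the matter, since neither names supplements.

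**2. The plan's own sample size.** Inputs from section 12.1: change 0.5, SD 1, paired two-sided t-test, alpha 0.05, power 90%. The noncentrality is 0.5/1 × √44 = 3.317 with 43 df. The exact power is 0.900, and with 43 nails it is 0.893. The stated 44 reproduces, as do the other five table cells. This figure is not in dispute; it fixes the test and scale used below.

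**3. Shift in the PRP mean.** The documents give no figure for supplement use or effect, so both are assumed. Let k of 10 participants have a shift b on every nail, with b = 0.5 (the change used in section 12.1) and no PRP effect. The spurious mean change is k × b / 10:

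- k = 2: 2 × 0.5 / 10 = 0.10
- k = 4: 4 × 0.5 / 10 = 0.20

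**4. False-positive rate of the before/after test** (nominal 5%; simulated, total SD 1, 8 PRP nails per participant)

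| Analysis | k = 0 | k = 2 | k = 4 |
|---|---|---|---|
| 80 PRP nails, independent | 5% | 13% | 40% |
| 10 participant means, ICC 0.2 | 5% | 6 to 7% | 13 to 14% |

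The SD of a participant mean is √(0.2 + 0.8/8) = 0.548. Adding the average shift to everyone instead gives slightly higher rates from the noncentral t: 14.3% and 42.4% for nails, 8.1% and 17.9% for participants. The simulated rates are lower because a shift carried by only some participants adds between-person variance: (k/10)(1 − k/10)b² = 0.04 for k = 2 and 0.06 for k = 4.

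**5. PRP-minus-PPP contrast.** Take each participant's mean over 8 PRP nails minus the mean over 2 PPP nails. A shift equal on all ten nails cancels: b − b = 0. In simulation the mean bias is about 0 and rejection is 5% for k = 0, 2 and 4.

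**The case against.** The strongest reply is that the gap is an undefined term and nothing more. Several points in it stand.

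- A reader might infer that a biotin user complies with every rule. The documents do not support that. The wording any medication in sections 4.3 and 4.4 can be read to include a product that section 2.3 discusses as a treatment. Unclear is not the same as permitted.
- A reader might infer that use would go unrecorded. That is not established either. Medications are reviewed at screening, scheduled at every visit, charted throughout, and assessed at discontinuation. What is missing is a prompt that names supplements.
- A reader might infer that the effect could never be examined. But section 12.1 already plans a before/after comparison in the PPP nails, where an equal shift would also appear. That check is weak: with 20 independent nails and SD 1 the standard error is 1/√20 = 0.22, larger than a shift of 0.10 or 0.20. It also would not show why those nails had improved.
- The 0.5 shift is an assumption, and section 2.3 calls biotin poorly studied. The 13% and 40% also require independent nails. At ICC 0.2 the nail-level test already rejects about 20% of the time with no supplement use, and about 27% and 45% with it, so much of that excess is clustering, which is a separate matter.
- Stable use from well before baseline adds little to a change from baseline.

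The reply does not remove the point. The planned primary test has no step that takes out a systemic shift, and the instructions to staff do not ask for the information needed to recognise one.

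**Conclusion.** The point holds as an ambiguity in scope and capture. It is not a demonstrated loophole. The protocol names biotin as a suggested treatment, leaves open whether its medication rules cover oral supplements, and relies on a before/after test that would credit any such effect to PRP.

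Only supplements started around baseline, or still building up then, matter. The size is unknown. Under an assumed 0.5 shift in 2 or 4 of 10 participants with no PRP effect, false positives are about 13% and 40% with independent nails, and about 6 to 7% and 13 to 14% on participant means with ICC 0.2. At the lower level of use, the participant-level rate is close to nominal. The misattribution comes as much from the missing PRP-versus-PPP test as from the restriction list. This is an inexpensive improvement and does not invalidate the trial.

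**What to change.** 1. Reconcile sections 3.1, 4.3 and 4.4, and state explicitly whether the existing restriction covers oral supplements such as biotin, before and during the study. Which way to decide is for the sponsor.
2. Whatever is decided, extend the review and recording in section 6.1.2, section 7.8 and Table 1 to medications, supplements and cosmetics, with start dates, at screening and Visits 1 to 4. Start dates separate stable use from recent use.
3. Add a within-participant PRP-minus-PPP contrast to section 12.1. It removes any systemic shift that is equal across nails, whether or not it was recorded.

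**Cost.** Items 1 and 2 need a few words in each section and one more question per visit. If the restriction is held to cover supplements, a few users may be excluded or delayed. Item 3 needs no new data but is less precise, because it rests on two PPP nails per participant. At SD 1 and ICC 0.2 its standard error is √[0.8 × (1/8 + 1/2)]/√10 = 0.22, against 0.548/√10 = 0.17 for the participant-level before/after mean.

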4.5 Screen Failures

Screen failures are defined as participants who consent to participate in the clinical trial but are not subsequently randomly assigned to the study intervention or entered in the study. A minimal set of screen failure information is required to ensure transparent reporting of screen failure participants, to meet the Consolidated Standards of Reporting Trials (CONSORT) publishing requirements and to respond to queries from regulatory authorities. Minimal information includes demography, screen failure details, eligibility criteria, and any serious adverse event (SAE).

Individuals who do not meet the criteria for participation in this trial (screen failure) because of a <specify modifiable factor> may be rescreened. Rescreened participants should be assigned the same participant number as for the initial screening.

4.6 Strategies for Recruitment and Retention

Patients attending Weil Cornell Medicine, Department of Dermatology, specialized nail clinic run by PI [name], with signs and symptoms of brittle nail syndrome will be targeted. 10 participants will be included in the study and approximately 20 patients will be screened. All participants will be enrolled in one of two U.S. locations:

Weill Cornell Dermatology - [name]

In the present study, participants will not be compensated or provided any incentives.

5. Registration Procedures

5.1 Subject Registration (WCM only)

Subjects will be registered within the WRG-CT as per the standard operating procedure for Subject Registration.

6. Study Procedures

6.1 Schedule of Assessments

Table 1. Schedule of trial event

	Screeni ng visit	Visit 1: Wk 0 or 2	Visit 2: Wk 4 or 6	Visit 3: Wk 8 or 10	Visit 4: Wk 12 or 14	Off Study ^d
Agent Administration		Х	X	Х		
Informed consent	Х					
Demographics	Х					
Medical history	Х					
Physical exam	Х	Х	X	Х	Х	Х
Concurrent medications	Х	X	X	Х	X	

Obtain nail clipping sample	Х					
Adverse event evaluation		X	X	Х	X	
Digital photographs	Χ	Х	X	X	X	
Patient satisfaction survey					Х	
Efficacy assessment						Х

6.1.1 Screening Visit (visit 1)

Screening visit

During the screening visit, all inclusion and exclusion criteria will be reviewed. Obtaining patient consent, history and review of medications will take place. A nail clipping will be obtained for those patients that have not had a negative histopathology result for onychomycosis within the past 6 months. If the patient has had a previous nail clipping within the past 6 months, that will suffice. Therefore, for some patients Visit 1 can take place on the same day of the Screening Visit, while for others Visit 1 will take place on week 2 (after a negative histopathology result for onychomycosis is received).

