The Principal Investigator will utilize the Physician Global Assessment (PGA) score for screening purposes during the screening/baseline visit to determine eligibility. The PGA will be comprised of five components: lamellar splitting, transverse splitting, ridging and longitudinal groove, longitudinal splitting, and nail thickness. Lamellar splitting, which represents onychoschizia, is defined as distal furrows or splits encompassing the distal nail plate involving the complete free edge of the nail plate. The second component, transverse splitting, is described as horizontal splitting from the free edge of the nail plate- with at least 2 or 3 horizontal splits of the distal nail plate. The third component, ridging and longitudinal grooves, is defined by at least 50% of the nail plate showing deep ridges and corresponding grooves. The fourth component, longitudinal splitting, which represents onychorrhexis, is defined as at least one deep longitudinal split of the entire nail plate. The fifth component, nail thickness, is defined by a clearly visible change in nail thickness. The presence of each of these components during the screening/baseline visit will represent 1 point on a scale. The inclusion criterion requires patients to have a score of at least 2 out of a maximum of 5 points.

The components used in the PGA assessment have been based on the scoring system used by Van der Kerkhof et. Al in their study, "Brittle nail syndrome: A pathogenesis-based approach with a proposed grading system". In this study, a grading system of 0-3 was used for each component, with 0-none, 1-mild, 2-moderate, 3-severe. The scale used for screening in the present study mirrors the moderate (score of 2) criteria used in the study by van der Kerkhof et. Al.

The Nail Superficial Abnormality Index (NSI):

The surface of the nails is divided into four quadrants, and each quadrant is scored for four parameters, namely, pitting, discoloration, longitudinal ridging and horizontal ridging. The presence or absence of any of these four parameters is scored as 1 or 0, respectively. Thus, the maximum possible score for a nail is 16 and minimum is 0.

Adverse Events and Reporting

Adverse events (AE) assessment will be ongoing throughout the study. All adverse events shall be reported by the clinical Investigator to the IRB as described below.

Adverse Device Effect (ADE)

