7.11 Measures to Minimize Bias: Randomization and Blinding

Computer software will be used to randomly generate a randomization table. 8/10 fingernails will be randomly allocated to treatment with PRP and the remaining 2 fingernails will receive injections with PPP. Randomization for each participant will be done on the same day of their first treatment, after all inclusion and exclusion criteria, including a negative histopathology report for onychomycosis are fulfilled. For the present study, treatment will be open label with respect to patient and investigators but is blinded to the endpoint committee. High quality images will be obtained utilizing a Canon camera and reviewed by an independent blinded endpoint committee (3 dermatologists with expertise in nails disease [name], [name], and [name] [name]) for PGIA (Physician Global Improvement Assessment.

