12.1 Study Design/Endpoints

For study design, please see section 3. Study Design.

Endpoints

The Primary efficacy endpoint will be the Physician Global Improvement Assessment (PGIA), which will be compared between follow-up point (week 12 - 14) and baseline point for nails with PRP injection, and between follow-up point (week 12 - 14) and baseline point for nails without PRP injection. The power analysis estimated that with approximately 44 nails with PRP injection enrolled in the study, a score change of 0.5 from baseline to week 12 – 14 can be detected through paired two-sided t-test with 90% power at 0.05 significant level for PRP group. The calculation assumed a standard deviation of 1 in scores. PGA is a novel tool that there is not enough reference to assume an accurate standard deviation, so the sample size estimation was also performed on a range of sd assumption. With assumption of sd in range of 0.5 to 1, 13 to 97 nails would be needed for the PRP injection group to detect a score change of 0.5 from baseline to week 12 - 14 through paired two-sided t-test with 90% power at 0.05 significant level.

Sample size estimation summary given different settings of standard deviation and meaningful changes

	sd=0.5	sd=1	sd=1.5
Difference = 1	5	13	26
Difference = 0.5	13	44	97

Secondary

Subject reported assessments of nail health will be analyzed using descriptive statistics.

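### Two of the five scored nail signs lie at the free edge, but trimming before photographs is neither controlled nor recorded and the baseline image is not named, so a change in trimming habit can enter the primary result.

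*Combined protocol and SAP*

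**What the plan says.** Section 3.1, repeated in Section 10, builds the PGA from five signs: "The presence of each of these components during the screening/baseline visit will represent 1 point on a scale". Lamellar splitting is "distal furrows or splits encompassing the distal nail plate involving the complete free edge of the nail plate". Transverse splitting is "horizontal splitting from the free edge of the nail plate- with at least 2 or 3 horizontal splits of the distal nail plate". The other three (ridging over at least half the plate, a split of the whole plate, and thickness) are not defined at the free edge.

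The named primary endpoint is the PGIA, "which encompasses observed improvement of lamellar splitting, transverse splitting, ridges and longitudinal grooves, longitudinal splitting, and nail thickness of target nails" (Section 3.1). Sections 10 and 10.1 instead describe response as change in the PGA. Under Section 6.1.3 the committee judges improvement from photographs.

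Section 12.1 has the score "compared between follow-up point (week 12 - 14) and baseline point for nails with PRP injection", and makes the same comparison separately for nails without PRP. It plans no contrast between the two. Section 7.11 says "treatment will be open label with respect to patient and investigators but is blinded to the endpoint committee".

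On clipping, Section 6.1.1 says: "A nail clipping will be obtained for those patients that have not had a negative histopathology result for onychomycosis within the past 6 months". It adds: "If the patient has had a previous nail clipping within the past 6 months, that will suffice". Patients in the second group may have Visit 1 on the screening day; the others start at week 2. Table 1 schedules photographs at screening, at Visit 1 and at each later visit.

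The nail-care rules (Sections 3.1, 4.3 and 4.4) concern medication and cosmetic products. The only image-handling rule is exposure correction (Section 3.1). Section 6.1.2 lists patient instructions at Visit 1 without giving their content.

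**The concern.** A split at the free edge can disappear in two ways: the nail improves, or someone cuts it off. A photograph does not separate the two unless free-edge length is comparable at both time points. Masking the readers does not help, because the nail itself has changed.

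The design offers little protection. The primary test is before versus after within PRP nails, so any net change in trimming between the two photographs is counted with the treatment effect. Patients know which two nails received PPP, so trimming could also differ by arm. With two candidate baseline images, one possibly taken before a clipping and one after it, two analysts could follow the plan and obtain different changes for the same nail.

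**Working it through.** **1. The plan's own figure.** Inputs from Section 12.1: change 0.5, SD 1, paired two-sided t-test, alpha 0.05, power 90%. Power is P(|T| > t with n − 1 df at 0.975), where T is noncentral t with noncentrality change × √n / SD. At n = 44 the noncentrality is 0.5 × √44 / 1 = 3.32 and power is 0.900, so the stated 44 is reproduced. The other five cells of the table (5, 13, 26, 13, 97) also reproduce. With the 80 PRP nails of Section 12.2, power for 0.5 is 0.993, and the change detectable with 90% power is 0.37. These figures treat nails as independent, as the plan does.

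**2. What trimming does to the mean.** Let k be the points removed from a trimmed nail (at most 2 of 5). Let q0 and q1 be the shares of nails with those signs cut away at baseline and at week 12–14.

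Spurious mean improvement = k × (q1 − q0).

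If q1 = q0, the shift is zero whatever the share. Only a net difference produces bias, and its sign follows the sign of q1 − q0.

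**3. Illustration of a net one-way loss.** The shares are assumptions; the documents give none. The last column is the probability that the planned PRP test rejects with no PRP effect (80 nails, SD 1, nominal level 0.05).

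| Net share q1 − q0 | Points k | Mean shift | Probability of rejection |
|---|---|---|---|
| 10% | 1 | 0.10 | 0.143 |
| 10% | 2 | 0.20 | 0.424 |
| 25% | 1 | 0.25 | 0.598 |
| 15% | 2 | 0.30 | 0.755 |
| 50% | 1 | 0.50 | 0.993 |
| 25% | 2 | 0.50 | 0.993 |

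**4. Illustration of balanced trimming.** Suppose one point is cut away in 25% of nails at each time, independently, and the planned SD of 1 does not already include this. The added variance is 2 × 0.25 × 0.75 = 0.375, so the SD becomes √1.375 = 1.17. The detectable change with 80 nails rises from 0.37 to 0.367 × 1.17 = 0.43. That is noise, and modest.

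**5. The screening clip alone.** The text speaks of one clipping. Assume one digit per clipped patient. If all ten patients are clipped, 10 of 100 nails are affected, or on average 8 of 80 PRP nails (10%). If half are clipped, it is 4 of 80 (5%). The direction depends on the baseline image:
- Screening photograph, taken before the clip: a removed split can count as improvement, if it has not returned by week 12–14.
- Visit 1 photograph, taken after the clip: that nail starts better, which works against improvement.

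**6. Trimming unrelated to arm.** In a simulation of 10 patients with 8 PRP and 2 PPP nails each (10,000 runs per setting), a within-patient PRP-minus-PPP contrast rejected in 0.045 to 0.054 of runs, close to nominal. Trimming that differs by arm would not cancel in such a contrast.

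**The case against.** The strongest reply is that trimming happens before baseline too. If habits are stable, the expected shift is zero, and nothing in the documents suggests more trimming before Visit 4. This stands: bias needs a net difference, and the rejection rates in the table are conditional on one.

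A reader might infer that the screening clip itself manufactures improvement. The documents do not support that. The clip probably touches few nails, the endpoint image comes 12 to 14 weeks later, and with a Visit 1 baseline the effect runs the other way. Nor is clipped versus unclipped patients a planned comparison.

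A reader might also infer that trimming could explain the whole planned 0.5. That is arithmetic on assumed shares, and on the PGA count. The named endpoint is the PGIA, whose scale is not given, and expert readers need not score a visibly shortened edge as improvement.

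Two further replies carry some weight. The separate PPP comparison would show arm-neutral trimming informally, though no test uses it. And the patient instructions may cover trimming, since their content is not stated; the absence of a rule is read from silence. Trimming that differs by arm is possible under open label, but no section shows that it occurs or in which direction.

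What remains is that an alterable part of the endpoint is left uncontrolled and unrecorded in an open-label before–after comparison, with two candidate baselines.

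**Conclusion.** The point holds as a design improvement worth making, not as evidence that the result will be biased. Two of the five signs can be removed by cutting, nothing in the documents makes trimming comparable at baseline and week 12–14, and the within-arm test passes any net difference into the primary result. Direction and size cannot be determined from the documents. The range of 0.1 to 0.5 points rests on assumed net one-way loss and PGA-type counting; similar trimming at both times gives mainly noise. The screening clip is the smaller part of the problem. If trimming is not recorded during the trial, the analysis cannot recover it afterwards.

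**What to change.** - **Sections 6.1 and 12.1:** name the Visit 1 pre-injection photograph as the baseline image for every participant.
- **Section 6.1.1 and the case report form:** record which digit was clipped at screening. In Section 12.1 add a sensitivity analysis that omits that digit.
- **Patient instructions (Section 6.1.2):** ask for no cutting or filing of any fingernail for the same fixed interval before Visit 1 and before Visit 4, with all ten nails treated alike. The documents give no basis for a particular interval, so the investigator should choose and state one. Patients starting at week 2 need this instruction at screening, because the instructions are now listed only at Visit 1.
- **Same-day starters:** record the date of last trimming and reproduce that interval before Visit 4.

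Do not require all ten nails to be cut before baseline. That would remove free-edge signs the trial needs at baseline in order to show improvement, after eligibility was scored with them present.

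The cost is a short no-trim interval for participants, one or two form fields, and possibly a short wait for some same-day starters. Sample size and treatment procedures are unchanged.
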